## **SPONSOR PERSONNEL**

# SYNOPSIS

Protocol Title:A Phase 4, Single-Center, Open-Label Study Evaluating th of the Nasal Guide Utilized During Administration with Ty		
Protocol Number:	OPP-009	
Study Treatment	Tyrvaya ® (varenicline solution 0.03 mg) Nasal Spray Administered with the Nasal Guide	
Study Objective:	Primary objective	
	To determine the safety of the nasal guide when utilized to aid in the administration of Tyrvaya ® (varenicline solution 0.03 mg) Nasal Spray	
	Overall Study Design	
Methodology:	This is a single center study. Subjects will be provided the nasal guide to utilize with Tyrvaya ® administration. 30 subjects will participate in this study.	
Duration:	This study will consist of two visits over 7 days.	
Controls:	Not applicable this is an open-label sub-study	
Dosing Regimen:	sing Regimen: Subjects will administer Tyrvaya ® BID with nasal guide for 7 days	
Summary of Visit Schedule	Nasal guide will be used to aid in the administration of Tyrvaya ® (varenicline solution 0.03 mg) Nasal Spray	
	At Visits 1 and 2, subjects will attach the nasal guide and administer one spray of Tyrvaya ® (varenicline solution 0.03 mg) nasal spray in each nostril. In between study visits, subjects will administer one spray of the nasal spray in each nostril twice daily (BID) approximately 12 hours apart at home using the nasal guide.	
Measures Taken to Reduce Bias:	Not applicable. This is an open label study.	

Study Population Characteristics		
Number of Subjects:	30 subjects	
Condition/Disease:	Dry Eye Disease	
Inclusion Criteria:	Subjects must:   1. Be at least 18 years of age   3. Have provided verbal and written informed consent.   5. Willing to comply with all study related visits and procedures	
Exclusion Criteria:	None	
Study Endpoints:	

Primary endpoints

Incidence of adverse events

	
Safety Measures:	Adverse Events	
Statistical Methods:		
Summary of Known and Potential Risks and Benefits to Human Subjects		

Refer to the Tyrvaya® Package Insert regarding the risks and benefits to human subjects. There are no known risks associated with the use of the nasal guide

Appendix 1: Nasal Guide Instructions for Use		
Appendix 2: Schedule of Visits And Measurements		
Appendix 3: Sponsor Approvals		
Appendix 4: Investigator's Signature		

Abbreviation	Term
AE	Adverse event
BID	Twice a Day
CFR	Code of Federal Regulations
CRF	Case report form
eCRF	Electronic Case Report Form
HIPAA	Health Information Portability and Accountability Act
ICF	Informed consent form
ICH	International Conference on Harmonization
IFU	Instructions for Use
IRB	Institutional Review Board
MedDRA	Medical Dictionary for Regulatory Activities
Mg	Milligram
PI	Package Insert
PT	Preferred Term
SAE	Serious adverse event
SAP	Statistical Analysis Plan
SOC	System Organ Class
TEAE	Treatment-emergent adverse event
US	United States

# LIST OF ABBREVIATIONS

# 1 NASAL GUIDE

# **2 STUDY OBJECTIVES**

To determine the safety of the nasal guide during administration of Tyrvaya® (varenicline solution 0.03 mg) Nasal Spray.

# **3** CLINICAL HYPOTHESIS

This study is testing the hypothesis that the use of the nasal guide with Tyrvaya® does not introduce any additional safety concerns as compared to the safety of Tyrvaya® alone.

# **4 OVERALL STUDY DESIGN**

This is a single center, open-label study to evaluate the safety of the nasal guide during administration of Tyrvaya® (varenicline solution 0.03 mg) Nasal Spray.

This study will consist of two visits over 7 days.

At Visits 1 and 2, the subjects will attach the nasal guide and administer one spray of Tyrvaya® (varenicline solution 0.03 mg) nasal spray in each nostril. In between study visits, subjects will administer one spray of the nasal spray in each nostril twice daily (BID) approximately 12 hours apart at home using the nasal guide.

# **5 STUDY POPULATION**

# 5.1 Number of Subjects

30 subjects will be enrolled at one study site in the United States (US).

# 5.2 Study Population Characteristics

All subjects must be at least 18 years of age, of any gender and race and must meet all inclusion criteria and none of the exclusion criteria.

### 5.3 Inclusion Criteria

- 1. Be at least 18 years of age.
- 3. Have provided verbal and written informed consent.
- 5. Willing to comply with all study related visits and procedures.

# 5.4 Exclusion Criteria

Not applicable

# 5.5 Withdrawal Criteria

If at any time during the study the Investigator determines that a subject's safety has been compromised, the subject may be withdrawn from the study, but will be followed for safety for the duration of the study, unless they refuse to attend follow-up visits.

A subject may withdraw consent from the study at any time.

The Sponsor and/or the Investigator may discontinue any subject from study treatment for noncompliance or for any valid medical reason during the study (see Section 8.6.2).

# **6 STUDY PARAMETERS**

#### 6.1 **Primary Endpoint**

• Incidence of adverse events

#### 6.2 Safety Measures

• Adverse events

# 7 STUDY MATERIALS

# 7.1 Nasal Guide

Subjects will be provided the nasal guide for use when administering Tyrvaya®. See Appendix 1 for Instructions for Use.

# 7.2 Tyrvaya®

Please see Tyrvaya package insert for additional information.

# 8 STUDY METHODS AND PROCEDURES

### 8.1 Subject Entry Procedures

#### 8.1.1 Overview

Subjects as defined by the criteria in Section 5.2, Section 5.3 and Section 5.4 will be considered for entry into this study.

#### 8.1.2 Informed Consent

Prior to a subject's enrollment in the trial (i.e., prior to any study-related procedures), the study will be discussed with each potential subject and subject wishing to participate must be administered and provide written informed consent using an Institutional Review Board (IRB)-approved informed consent form (ICF). The ICF must be the most recent version that has received approval by a properly constituted IRB.

#### 8.1.3 Washout Intervals

There are no washout intervals for this study.

#### 8.1.4 **Procedures for Final Study Entry**

Subjects must meet all inclusion criteria.

#### 8.1.5 Methods for Assignment to Treatment Groups

Not applicable as this is an open label study.

# 8.2 Concomitant Therapies

The use of any concurrent medication, prescription or over the counter, is to be recorded on the subject's source document and corresponding eCRF along with the reason the medication was taken.

#### 8.2.1 **Prohibited Medications**

There are no prohibited medications for this study.

#### 8.2.2 Escape Medications

No escape medications are required for this study.

#### 8.2.3 Special Diet or Activities

No special diets or activity is required for this study.

#### **8.3 Examination Procedures**

#### 8.3.1 Procedures to be Performed at Each Study Visit with Regard to Study Objectives(s)

The following procedures will be performed (see Appendix 2 for description).

The nasal guide will be used when administering Tyrvaya®. At Visits 1 and 2, subjects will attach the nasal guide and administer one spray Tyrvaya® in each nostril. In between study visits, subjects will administer one spray of the nasal spray in each nostril twice daily (BID) approximately 12 hours apart at home using the nasal guide.

#### Visit 1 (Day 1): Screening and Enrollment

- Informed consent/Health Information Portability and Accountability Act (HIPAA) consent
- Demographic data, medical history, prior medication (s), and ocular history
- Eligibility Criteria
- Enrollment
- Review Tyrvaya® Instructions for Use (IFU)
- Dispense nasal guide and IFU
- Subject Administration of Tyrvaya® with nasal guide
- Adverse Event Query

#### Tyrvaya® Clinical Trial Protocol: OPP-009

#### Visit 2 (Day 7)

- Subject administration of Tyrvaya® with nasal guide
- Concomitant Medications
- Adverse Events Query

#### **Early Termination**

- Concomitant Medications
- Adverse Event Query

### 8.4 Schedule of Visits, Measurements and Dosing

#### 8.4.1 Scheduled Visits

Refer to Appendix 1 for a schedule of visits and measurements.

#### 8.4.2 Unscheduled Visits

These visits may be performed to ensure subject safety. All procedures performed at an unscheduled visit will be recorded in the source documents and on the Unscheduled Visit eCRF pages. Any procedure indicated in the eCRF that is not performed should be indicated as "Not done."

Evaluations that may be conducted at an Unscheduled Visit include:

- Assessment of AEs
- Any other assessments needed in the judgment of the Investigator.

#### 8.5 Compliance with Protocol

Subjects will be instructed on the proper use and storage of the nasal guide and provided with written instructions for use at Visit 1.

#### 8.6 Subject Disposition

#### 8.6.1 Treatment Completed Subjects

A Completed Subject is one who has completed Visit 1 and Visit 2.

#### Tyrvaya® Clinical Trial Protocol: OPP-009

#### 8.6.2 Discontinued Subjects

Subjects may be discontinued from treatment, or from involvement in the study at any time prior to their completion of the study due to:

- Non-fatal adverse event
- Protocol violations
- Disease progression
- Lost to follow-up.
- Physician decision
- Subject non-compliance
- Death
- Study terminated by the Sponsor
- Withdraw by subject (e.g., withdrawal of consent); and
- Other

Note: In addition, any subject may be discontinued from treatment or from study involvement for any sound medical reason at the discretion of the Investigator (after consultation with the Sponsor) or the Sponsor.

Notification of a subject discontinuation and the reason for discontinuation will be made to the Sponsor and will be clearly documented on the eCRF.

If a subject discontinues from treatment, the subject will be asked to be followed for safety for the duration of the study, unless they refuse to attend follow-up visits.

Discontinued subjects may be replaced.

#### 8.7 Study Termination

The study may be stopped at any time by the Investigator and/or Sponsor, with appropriate notification.

#### 8.8 Study Duration

An individual subject's participation will involve 2 visits over 7 days.

#### 8.9 Monitoring and Quality Assurance

9 SAFETY DEFINITIONS, MONITORING AND REPORTING

#### 9.1 Adverse Events

An adverse event (AE) is defined as any untoward medical occurrence associated with the use of a drug or device in humans, whether the event is considered drug or device related or not. An AE can therefore be any unfavorable and unintended sign (e.g., an abnormal laboratory finding), symptom, or disease occurring after the subject started dosing with the device, without any judgment about causality. Any pre-existing medical condition that worsens after administration of the nasal guide will also be considered a new AE.

AE collection will start following the first administration of Tyrvaya® utilizing the nasal guide until the last follow up visit of the study.

Documentation regarding the AE should be made as to the nature, date of onset, end date, severity, relationship to study drug, action(s) taken, seriousness, and outcome of any sign or symptom observed by the Investigator or reported by the subject upon indirect questioning.

#### 9.1.1 Severity

Severity of an AE is defined as a qualitative assessment of the degree of intensity of an AE as determined by the Investigator or reported to him/her by the patient/subject. The assessment of severity is made irrespective of relationship to study drug or seriousness of the event and should be evaluated according to the following scale:

- *Mild:* Event is noticeable to the subject but is easily tolerated and does not interfere with the subject's daily activities.
- *Moderate*: Event is bothersome, possibly requiring additional therapy, and may interfere with the subject's daily activities.
- *Severe*: Event is intolerable, necessitates additional therapy or alteration of therapy, and interferes with the subject's daily activities.

#### 9.1.2 Relationship

The relationship of each AE to the investigational product should be determined by the Investigator (in a blinded manner) using these explanations:

- *Definite:* When there are good reason and sufficient documentation to demonstrate a direct causal relationship between investigational product and AE
- *Probable:* When there are good reasons and sufficient documentation to assume a causal relationship in the sense of plausible, conceivable, likely but not necessarily highly probable

Tyrvaya® Clinical Trial Protocol: OPP-009

- *Possible:* When there is sufficient information to accept the possibility of a causal relationship in the sense of not impossible and not unlikely, although the connection is uncertain or doubtful, for example, due to missing data or insufficient evidence.
- *None:* When there is sufficient information to accept a lack of a causal relationship, in the sense of impossible and improbable.
- *Unclassified:* When the causal relationship is not assessable for whatever reason due to insufficient evidence, conflicting data, or poor documentation.

#### 9.1.3 Expectedness

The expectedness of an AE should be determined based upon existing safety information about the study drug using these explanations:

- *Unexpected:* An AE that is not listed in the Investigator's Brochure (IB) or is not listed at the specificity or severity that has been observed.
- *Expected:* An AE that is listed in the IB at the specificity and severity that has been observed.
- *Not Applicable:* Any AE that is unrelated to the study drug.

AEs that are mentioned in the Package Insert (PI) as occurring with a class of drugs or as anticipated from the pharmacological properties of the drug but are not specifically mentioned as occurring with the drug under investigation are to be considered unexpected.

The Investigator should initially classify the expectedness of an AE, but the final classification is subject to the Medical Monitor's determination.

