8.1 General Consideration

All data, including demographic and baseline characteristics and endpoint measures, will be summarized descriptively. Continuous variables will be summarized using the number of subjects (n), mean, SD, median, 25th and 75th percentiles, and minimum and maximum. Categorical variables will be summarized with frequency and percentage.

For the summaries, medical history and AEs will be coded using version 26.0 of the MedDRA dictionary.

All collected data will be presented in listings which will be sorted by subject ID and visit when it is appropriate. Summaries and data listings will be generated using SAS[®] Version 9.4 or higher.

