8.10 Safety Analysis

8.10.1 Adverse Event

The investigator will promptly review each Adverse Event (AE) for accuracy and

completeness, and classify each AE according to its intensity, its re

administration procedure, and its seriousness. AEs will be coded using version 26.0 of the MedDRA dictionary. AEs will be monitored throughout the study and documented on the appropriate AE form. AEs will be categorized as ocular and non-ocular events as well as by system organ class (SOC) and preferred term (PT), seriousness, severity, and relation to study medications.

All treatment-emergent adverse events (TEAEs) will be summarized. A TEAE is defined as an AE that is new or worsened in severity compared to the first dose of study drug.

TEAEs will be summarized by subject. In addition, the number of TEAE episodes that occurred during the study will be provided in the overall summary of AE table. All AEs will be presented in data listing with a flag indicating the event is a TEAE.

The following presentations of TEAEs will be generated:

- Overall adverse events summary (including any TEAEs, ocular TEAEs, resolved ocular TEAEs, non-ocular TEAEs, SAEs, treatment emergent SAEs, treatment-related treatment emergent SAEs, TEAEs by maximum severity, TEAEs by relationship to study drug, AEs leading to treatment/study discontinuation)
- All TEAEs by SOC and PT
- All ocular TEAEs by SOC and PT
- All non-ocular TEAEs by SOC and PT
- Resolved ocular TEAEs by SOC and PT
- Serious adverse events (SAE) by SOC and PT
- Serious treatment-emergent adverse events (TESAE) by SOC and PT
- Related treatment-emergent serious adverse events (TESAE) by SOC and PT
- TEAEs by SOC and PT and by severity
- TEAEs by SOC and PT and by relationship
- TEAEs by SOC and PT leading to treatment discontinuation
- TEAEs by SOC and PT leading to study discontinuation

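### Does Protocol 9.1.3 need rewording because an adverse event due to the nasal guide alone fits two expectedness categories?

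*Protocol*

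**What the plan says.** Protocol 9.1.3 bases expectedness on safety information about the study drug. *Unexpected* is "An AE that is not listed in the Investigator's Brochure (IB) or is not listed at the specificity or severity" observed. *Expected* is the reverse: listed in the IB as observed. *Not Applicable* is "Any AE that is unrelated to the study drug". A further sentence deals with class effects in the package insert. The investigator classifies first, but "the final classification is subject to the Medical Monitor's determination". The nasal guide is not mentioned in the section.

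Elsewhere the guide is central. Protocol 2 makes its safety the objective, and the SAP synopsis names it as the investigational product. The Protocol synopsis gives the study treatment as Tyrvaya administered with the guide. Causality is judged against yet another term: "The relationship of each AE to the investigational product should be determined by the Investigator" (Protocol 9.1.2). The hypothesis in Protocol 3 is that the guide "does not introduce any additional safety concerns as compared to the safety of Tyrvaya" alone.

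**The concern.** The categories in 9.1.3 use two different criteria. *Unexpected* and *Expected* ask only whether the event is listed. *Not Applicable* asks only whether it is unrelated to the drug. An event due to the guide and not to the drug therefore meets two of the three definitions, and neither document says which prevails.

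Such events are in scope. The AE definition in Protocol 9.1 covers device-related events, and 10.3.2 allows for a relationship to the administration procedure as well as to the drug. With the SAP's meaning of investigational product, an event could be rated definitely related under 9.1.2 and still be *Not Applicable* under 9.1.3. It would then fall outside 9.3.1, which concerns events that are both suspected and unexpected. If that label governed reporting or fed the main comparison, a new problem with the guide could be missed in a study set up to find one.

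**Working it through.** No arithmetic is needed beyond counting. There are two checks: what the definitions say when applied, and what depends on the result.

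**1. Applying the definitions**

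| Event | Literal reading | *Not Applicable* applied first |
|---|---|---|
| Drug-related, listed in IB as observed | *Expected* | *Expected* |
| Drug-related, not so listed | *Unexpected* | *Unexpected* |
| Guide only, listed | *Expected* and *Not Applicable* | *Not Applicable* |
| Guide only, not listed | *Unexpected* and *Not Applicable* | *Not Applicable* |
| Unrelated to drug and guide, listed | *Expected* and *Not Applicable* | *Not Applicable* |
| Unrelated to drug and guide, not listed | *Unexpected* and *Not Applicable* | *Not Applicable* |

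Two things follow. The overlap is not specific to the guide: the last four rows behave alike. Also, every event is either listed as observed or not, so on the literal reading *Not Applicable* never applies by itself and has no function. A reader will take it as an exclusion made before listing is considered, and the overlap then disappears. The remaining gap is narrower: a guide-only event is not rated, because no reference for the guide is named in 9.1.3.

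This assumes that the study drug means Tyrvaya alone. If the term includes the guide, *Not Applicable* does not fit a guide-only event and there is no overlap for such events. The public text does not settle this. Section 1 of the Protocol, headed Nasal Guide, has no visible content, so the lack of a visible definition cannot be counted against the plan.

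**2. What depends on the label**

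- *Reporting of all AEs.* Protocol 9.3 sends every AE to the sponsor, and to the ethics body where its rules or the regulations require. Expectedness is not a condition.
- *Suspected and unexpected events.* Protocol 9.3.1 repeats that routing and sets no separate timeline. An event left out of 9.3.1 still goes by the same route under 9.3.
- *Serious events.* Protocol 9.3.2 applies the 24-hour rule to all SAEs, related to the device or not.
- *Tables.* Protocol 10.3.2 lists 6 AE presentations and SAP 8.10.1 lists 12. They are organised by ocular or non-ocular site, resolution, seriousness, severity, relationship, discontinuation, system organ class and preferred term. Expectedness appears in 0 of 6 and 0 of 12.
- *Primary endpoint.* The incidence of AEs counts an event whatever its expectedness.
- *Hypothesis.* Protocol 10.3 and the SAP synopsis assign the comparison with Tyrvaya alone to a descriptive comparison with the historical Integrated Summary of Safety. Expectedness has no part in it.
- *Listings.* The SAP states that "All collected data will be presented in listings which will be sorted by subject ID and visit when it is appropriate" and that "All AEs will be presented in data listing with a flag indicating the event is a TEAE". The label would be visible there only if it is recorded. The 8 items that Protocol 9.1 requires for each AE are "nature, date of onset, end date, severity, relationship to study drug, action(s) taken, seriousness, and outcome"; expectedness is not one of them.

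The only planned output that could differ between the readings is therefore one column of a listing, and the plan does not require that column to be filled.

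**The case for a change.** The best case for a change is this. The order of assessment is implied, not written. Naming the medical monitor says who decides, not by what rule. If *Not Applicable* is taken first, an event attributed to the object under study is never set against known safety information. The Protocol synopsis states no known risks from the guide, so any such event would be new information, and *Not Applicable* does not show that. The causality statement in 9.3.2 also names only the study drug. A few sentences would put this right.

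The textual points stand: 9.1.3 was written for a drug and not adapted to a device accessory. The consequence does not follow. A guide-attributed event still reaches the sponsor, still counts in the endpoint and still appears in the tables under its preferred term, where it can be compared with the historical data. The medical monitor also has a guide document to consult, since Protocol 11.5.1 refers to a nasal guide package insert.

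Nor is rewording as simple as it looks. Calling guide-only events unexpected unless a guide document lists them would clash with the *Expected* definition whenever the IB lists the same event. It would also leave the overlap in place for events unrelated to both drug and guide. And it presupposes separate attribution to drug and guide, whereas 9.1.2 provides one rating against one investigational product.

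**Conclusion.** No change is called for. The literal overlap exists, but the ordinary reading removes it, and it was never particular to the guide. What is left is a missing reference document for guide-attributed events, which the medical monitor can supply case by case. The effect is nil on reporting routes, on all 6 Protocol and 12 SAP presentations, on the primary endpoint and on the historical comparison. At most it touches a label in a listing.

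This rests on two assumptions: that the reporting sections are followed as written, and that no unpublished output uses expectedness. The documents give no frequency for events due to the guide alone, and the conclusion does not depend on one, because nothing planned changes however many occur.
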